### **Definition of Terms**

Investigational Product is defined as, “A pharmaceutical form of an active ingredient or placebo being tested or used as a reference in a clinical trial, including a product with a marketing authorization when used or assembled (formulated or packaged) in a way different from the approved form, or when used for an unapproved indication, or when used to gain further information about an approved use” (from International Conference on Harmonisation of Technical Requirements for Registration of Pharmaceuticals for Human Use [ICH] Harmonised Tripartite Guideline E6: Guideline for Good Clinical Practice).

The terms “Investigational Product” and “study drug” may be used interchangeably in the protocol.

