5 DEFINITIONS

5.1 Baseline

Baseline observable seizure frequency (see Section 5.7.1) from the seizure diary will be derived by measuring over approximately 6 weeks between the screening visit and the day prior to the randomization visit.

For all other measures, baseline value will be the last non-missing assessment prior to or on the date of the first dose of investigational product.

The baseline value will be used for all analyses of changes from the randomization visit and the phrases “change from baseline” and “change from randomization” will be used interchangeably.

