7.3 Unscheduled or Early Termination Visits

In general, data collected by study visit will be summarized using the visit number specified in the database. Outcomes scheduled at a planned study visit but collected during an unscheduled visit or early termination visit will be mapped into the closest study visit based on the study day of the unscheduled visit or early termination visit, and the schedule of events in the protocol.

For outcomes where both the planned study visit and an unscheduled visit or early termination visit corresponding to that study visit are available, the planned study visit measurement will be used for the analysis.

All safety data including the planned study visits and unscheduled/early termination visits will be included in the shift tables.

All data will be included in the data listings and outcomes measured during unscheduled visits and early termination visits will be marked as acquired during an unscheduled visit.

Observable seizure frequency will be mapped to visits as described in Section [5.7.1](#).

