8 STATISTICAL METHODS OF ANALYSIS

8.1 General Principles

During the Double-Blind Placebo-Controlled Treatment Period, efficacy analyses will be based on the Efficacy Analysis Set or the Per Protocol Analysis Set. During the open label period, efficacy analyses will be based on the Extension Set. Safety analyses will be based on the Safety Analysis Set. Unless stated otherwise, statistical tests will be 1-sided hypothesis tests performed at the 5% level of significance and confidence intervals will be 2-sided 90% confidence intervals. Continuous variables will be summarized by number of subjects and mean, standard deviation (SD), median, minimum, and maximum values. Categorical variables will be summarized by number and percentage of subjects.

Analyses and summaries by study period will be done for the following time periods:

- Double-blind placebo-controlled treatment period: after the date of the randomization visit until the date of the week 8 visit
- Open-label extension period: after the date of the week 8 visit until the date of the week 52 visit
- Dose exploration period: after the date of the week 26 visit until the date of the week 36 visit

Overall analyses and summaries will include all subjects and ignore treatment assignment.

For logarithmic transformations of seizure frequency, the natural logarithm will be used and a value of 1 will be added prior to performing the transformation.

For analyses and summaries of subjects while taking UX007, the time while taking placebo will be excluded and the original baseline will be used for all subjects regardless of which treatment was taken during the double-blind placebo-controlled treatment period.

Graphical displays of select study endpoints will be completed and include both observed study data and modeled analyses. Arithmetic means, least square means (LSM), and appropriate measure of dispersion (e.g., standard deviation, standard error) or confidence intervals may be displayed in figures.

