8.7 Safety Analyses

All safety analyses will be based on the Safety Analysis Set. In general safety analyses will be completed using summary statistics, graphs or subject listings. No planned inferential testing of safety endpoints is planned. If after the planned analysis it is determined by the medical writer and study medical monitor that inferential tests of significance may help to provide context for safety information these tests may be performed and identified in the CSR. Summaries will be done by study period and overall.

Analyses and summaries will be performed by study period, by treatment group, for subjects while taking UX007, and overall.

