8.7.1 Adverse Events

Adverse Events will be assessed at all visits and throughout the course of the study. An AE will be considered a treatment emergent adverse event (TEAE) if it occurs or worsens in severity on or after the date of the first dose of study drug. An AE will be considered a UX007 emergent adverse event if it occurs or worsens in severity on or after the first date of

first dose of UX007 during the study. It is expected that the date of first dose of UX007 during the study will be the date of Randomization visit for the UX007 group and the date of Week 8 visit for the placebo group; however, the date of first UX007 dose actually received will be used.

UX007 emergent AEs will be summarized by SOC and preferred term during the period exposed to UX007 by treatment group and overall for all subjects who receive UX007. TEAEs will be summarized by SOC and preferred term during the course of the study by treatment group and overall for all subjects who receive study drug.

Exposure adjusted event incidence, defined as total number of occurrences of an event summed across all subjects in the group divided by the total observed time for events for subjects in the group, will be summarized for TEAEs and UX007 emergent AEs by SOC and preferred term by treatment group and overall.

During the double-blind placebo-controlled period; TEAEs will be summarized by treatment group and overall, and UX007 emergent AEs will be summarized by treatment group and overall. If no placebo subjects also receive UX007 during the double-blind placebo-controlled period, then there will only be one group for UX007 emergent AEs during the double-blind placebo-controlled period. During the open-label extension period, TEAEs and UX007 emergent AEs will both be summarized by treatment group and overall.

A high-level safety summary will display the numbers of subjects who experience one or more AEs in each of the following categories:

- All TEAEs and UX007 emergent AEs
- All treatment related TEAEs and UX007 emergent AEs
- Serious TEAEs and UX007 emergent AEs
- All treatment related SAEs and UX007 emergent SAEs
- Grade 3/4 TEAEs and UX007 emergent AEs
- TEAEs and UX007 emergent AEs leading to study discontinuation
- Fatal TEAEs and UX007 emergent AEs
- TEAEs and UX007 emergent AEs in the GI SMQ (see [Appendix C](#))
- Related TEAEs and UX007 emergent AEs in the GI SMQ

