8.7.5 Select Clinical Laboratory Parameters

Clinical laboratory data will be summarized by the type of laboratory test. Reference ranges and markedly abnormal results will be used in the summary of laboratory data.

Summary statistics will be calculated for each laboratory analyte at baseline and at each scheduled time point. Changes from baseline results will be presented in pre- versus post-treatment cross tabulations (with classes for below, within, and above normal ranges). A listing of subjects with any markedly abnormal laboratory results will be provided. The frequency and percentage of subjects who experience abnormal clinical laboratory results (i.e., outside of reference ranges) and/or clinically significant abnormalities will be presented for each clinical laboratory measurement.

The following laboratory results will be summarized by time point for the observed value as well as for the change from baseline value:

- Chemistry: Alanine aminotransferase (ALT), Alkaline phosphatase, Aspartate aminotransferase (AST), Bilirubin (total), Blood urea nitrogen (BUN), Calcium, Chloride, Serum creatinine, Gamma-glutamyl transpeptidase (GGT), Serum glucose, Potassium, Protein (albumin and total), Sodium
- Hematology: Hematocrit, Hemoglobin, Platelet count, Red blood cell (RBC) count, White blood cell (WBC) count, Beta-hydroxybutyrate (BHB) (at Screening)
- Urinalysis: Appearance, Color, pH, Specific gravity, Ketones, Protein, Glucose, Pregnancy test (if applicable)

For fasting serum glucose, triglycerides, ALT, AST and GGT, CTCAE severity grades will be summarized in shift tables pairing each subject's baseline severity grade with the subject's highest post-baseline severity grade.

Specifically, CTCAE severity grades for increased triglycerides are:

- Grade 1: 150 – 300 mg/dL; 1.71 – 3.42 mmol/L
- Grade 2: > 300 – 500 mg/dL; > 3.42 – 5.7 mmol/L
- Grade 3: >500 – 1000 mg/dL; > 5.7 – 11.4 mmol/L
- Grade 4: >1000 mg/dL; > 11.4 mmol/L

CTCAE severity grades for hypoglycemia are:

- Grade 1: <LLN – 55 mg/dL; <LLN – 3.0 mmol/L
- Grade 2: <55 – 40 mg/dL; <3.0 – 2.2 mmol/L
- Grade 3: <40 – 30 mg/dL; <2.2 – 1.7 mmol/L
- Grade 4: < 30 mg/dL; <1.7 mmol/L

CTCAE severity grades for increased ALT and increased AST are:

- Grade 1: >ULN to 3.0 x ULN
- Grade 2: >3.0 x ULN to 5.0 x ULN
- Grade 3: >5.0 x ULN to 20.0 x ULN
- Grade 4: >20.0 x ULN

And CTCAE severity grades for increased GGT are:

- Grade 1: >ULN to 2.5 x ULN
- Grade 2: >2.5 x ULN to 5.0 x ULN

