- Grade 3: >5.0 x ULN to 20.0 x ULN
- Grade 4: >20.0 x ULN

Hy's Law criteria will be applied against test results. Subjects with serum total bilirubin >2 x ULN and ALT or AST >3 x ULN will be considered positive for Hy's law status. Results will be presented in shift tables. For Hy's Law, shift tables will be produced:

- Hy's Law negative at baseline, remaining Hy's Law negative throughout the study
- Hy's Law negative at baseline, becoming Hy's Law positive at any point during the study

- Hy's Law positive at baseline and Hy's Law negative throughout the study
- Hy's Law positive at baseline and Hy's Law positive at any point during the study

A data listing of all subjects who are Hy's Law positive will be produced.

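### On-UX007 laboratory and ECG shift tables keep the pre-placebo baseline, so a shift that began on safflower oil and persists is shown under UX007; a supplementary table for ex-placebo subjects would separate the two (low severity)

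*SAP*

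**What the plan says.** - **Baseline rule.** For any summary of subjects while on UX007, SAP 8.1 removes placebo time, but "the original baseline will be used for all subjects regardless of which treatment was taken during the double-blind placebo-controlled treatment period".
- **What that baseline is.** Apart from diary seizure frequency, SAP 5.1 says the "baseline value will be the last non-missing assessment prior to or on the date of the first dose of investigational product". The Protocol's Definition of Terms (Section 4) describes investigational product as "A pharmaceutical form of an active ingredient or placebo being tested or used as a reference in a clinical trial". The placebo arm's baseline is therefore set before, or on the day of, its first safflower oil.
- **Reach.** SAP 8.7 on safety states: "Analyses and summaries will be performed by study period, by treatment group, for subjects while taking UX007, and overall". Table 6 lists no separate on-UX007 shift table, so this general sentence is what creates the on-UX007 column.
- **Shift displays.** In SAP 8.7.5, "Changes from baseline results will be presented in pre- versus post-treatment cross tabulations", and CTCAE tables pair the baseline grade with the worst later grade. Table 6 adds an ECG shift table.
- **Adverse events.** UX007-emergent events are counted from the switch: under SAP 8.7.1, "the date of first UX007 dose actually received will be used". Laboratory and ECG shifts have no counterpart to this rule.

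**The concern.** A shift table headed as time on UX007 is read as a record of what changed on UX007. For subjects who spent Weeks 0 to 8 on safflower oil, the reference value lies on the far side of the placebo period. The Week 8 value, which would show whether the abnormality was already there at the switch, is left out as placebo time.

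The same change can then be classed in two ways. As an adverse event that began on placebo and did not worsen, it is not UX007-emergent. As a laboratory grade, it is a shift on UX007. What is at stake is the descriptive attribution of laboratory and ECG abnormalities in the pooled on-UX007 column, mainly those too small to be recorded as adverse events.

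**Working it through.** The plan gives no figure for this point, and its sample-size calculation plays no part in it. The check sets the rules side by side and then counts the exposed subjects.

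**1. Which values enter, for an ex-placebo subject** (Protocol 7.5.4.3, 7.5.4.5 and Table 2.1)

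| Measure | Usual baseline | Value at switch (placebo time, excluded) | First scheduled value on UX007 | Gap from switch |
|---|---|---|---|---|
| Laboratory | Week 0 | Week 8 | Week 26 | 26 − 8 = 18 weeks |
| ECG | Screening (Week −6) | Week 8 | Week 52 | 52 − 8 = 44 weeks |

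Unscheduled visits aside, only a change lasting 18 weeks (laboratory) or 44 weeks (ECG) after the switch can carry over.

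**2. What each baseline reports when the later value is abnormal**

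| Baseline | Week 8, on oil | Later, on UX007 | Original baseline | First-UX007-dose baseline |
|---|---|---|---|---|
| normal | normal | abnormal | shift | shift |
| normal | abnormal | abnormal | **shift** | **no shift** |
| abnormal | normal | abnormal | **no shift** | **shift** |
| abnormal | abnormal | abnormal | no shift | no shift |

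The two baselines disagree in rows 2 and 3. Row 2 credits UX007 with a change that began on oil. Row 3 hides a worsening on UX007. The rule can therefore err in either direction.

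**3. How many subjects are exposed**

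Inputs: about 40 subjects (SAP 3.1); the first 3 randomised 1:1 and the rest 3:1 (SAP 3.3).

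- Expected placebo: 3 × 0.5 + 37 × 0.25 = 10.75. Expected UX007: 40 − 10.75 = 29.25.
- All placebo subjects enter the extension: 10.75/40 = 26.9% of the pooled column.
- 80% enter (assumption): 10.75 × 0.8 = 8.6, and 8.6/(29.25 + 8.6) = 8.6/37.85 = 22.7%.

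**4. Weight of one carried-over subject who would not otherwise have shifted**

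- Pooled column: 1/40 = 2.5 points to 1/37.85 = 2.6 points.
- Ex-placebo column: 1/10.75 = 9.3 points to 1/8.6 = 11.6 points.

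These are weights per subject, not estimates of how many are affected. The documents give no rate of persisting placebo-period shifts. If that rate were 5% to 20% (an assumption with no source in the plan) and all placebo subjects entered the extension, 10.75 × 0.05 = 0.54 to 10.75 × 0.20 = 2.15 subjects would carry over. That is 0.54/40 = 1.3 to 2.15/40 = 5.4 points of the pooled column.

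**5. What the planned tables already recover**

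- Mean change since the switch can be approximated within the original placebo arm as the later visit minus Week 8.
- Shift counts cannot be subtracted in this way, because two separate tables do not show whether the same subject was abnormal at both times.
- The placebo arm's double-blind shift table does give an upper bound at scheduled visits. If it shows K shifted subjects, at most K can carry over, and K = 0 rules it out. When K is above zero, only the listings identify the subjects.

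**The case against.** The case for leaving the plan alone is substantial.

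- **The original baseline is a sound reference.** It is the only value taken off both oils, and a lasting abnormality really is present on UX007. This stands, and is why the planned tables should stay.
- **Most of the gap is covered.** Protocol 7.5.4.9 records clinically significant changes as adverse events, which then follow the first-UX007-dose rule. The by-period, by-arm tables bound carry-over, and the listings resolve it for about ten subjects. This stands and sets the severity. It leaves the pooled shift column itself unable to separate the two sources.
- **Plausibility is thin.** Protocol 5.3 names excessive weight gain, but for triheptanoin at high doses and not for safflower oil. Weight has no shift table, and its mean change is recoverable as in step 5. Nothing in the documents says safflower oil alters laboratory or ECG values. This stands, so no rate can be claimed.
- **Hy's Law adds almost nothing.** The table does count a subject as Hy's "Law positive at any point during the study". But subjects with ALT or AST above three times the upper limit at Screening are excluded, and every positive subject is listed individually.

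A reader might also infer that placebo time itself leaks into the on-UX007 shift tables, because SAP 7.3 says "All safety data including the planned study visits and unscheduled/early termination visits will be included in the shift tables". The documents do not support that. The sentence sits in a section on unscheduled and early termination visits and concerns visit type. The SAP 8.1 exclusion of placebo time is a general principle and governs.

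**Conclusion.** The point holds as a low-severity, cheap improvement. The stated rule places a laboratory reference-range, CTCAE-grade or ECG shift that arose on safflower oil and persists under UX007, and it can hide the reverse pattern. The ex-placebo subjects exposed to this make up 23% to 27% of the pooled column. That range rests on exactly 40 subjects, the stated allocation and the assumed 80% to 100% extension entry. The number actually affected is unknown.

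Two stronger conclusions are tempting and should not be drawn. One is that the plan systematically overstates UX007 toxicity: the rule can err either way, no rate is given, and SAP 8.7 plans no inferential safety testing. The other is that the main safety comparison is compromised: the double-blind comparison uses a common pre-treatment baseline, and UX007-emergent adverse events are dated from the first UX007 dose. Neither is touched, nor is the efficacy baseline.

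**What to change.** Keep every original-baseline table. For ex-placebo subjects only, add:

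1. laboratory shift tables, by reference range and by CTCAE grade, and an ECG shift table, with baseline defined as the last non-missing value on or before the first UX007 dose (normally Week 8) and only later values counted as post-baseline;
2. a footnote that this reference was taken on safflower oil, so a change that began on oil and was kept shows there as no shift.

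Limit the CTCAE table to analytes actually collected. SAP 8.7.5 names triglycerides and fasting glucose, but Protocol Table 7.5.4.5.1 has no triglycerides and Protocol 7.5.4.5 does not require fasting.

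Mean-change summaries from the switch, a Hy's Law count restricted to time after the first UX007 dose, and a sentence repeating the placebo-time exclusion are optional.

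The cost is one derived baseline, a few tables and a footnote. No new data are needed: laboratory tests and ECG are scheduled at Week 8, and open-label UX007 follows completion of that visit (Protocol 7.4). The downside is a slightly longer output package. Read alone, the new tables would hide sustained change that began on oil, so they supplement the planned ones and do not replace them.

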8.2 Subject Accountability

The number and percentage of subjects in each of the analysis populations (Screened, Randomized, Efficacy, Per Protocol, Safety, Extension, PK) will be summarized by treatment group and overall.

Screen-failure subjects (i.e., subjects screened but not randomized) and the associated reasons for failure to randomize will be tabulated overall for the Screened Population. The number and percentage of subjects in the Randomized Population who complete the

double-blind placebo-controlled treatment period, who complete the open-label extension period and who prematurely discontinue will be presented for each treatment group and overall. The reasons for early discontinuation will be summarized.

8.2.1 Protocol Deviations

Protocol deviations will be summarized for the Efficacy Analysis Set and listed by type.

8.3 Demographics

A table will be presented for the Efficacy Analysis Set by treatment group and overall for the following variables:

- Ethnicity
- Race
- Age at informed consent and age group using the following categories:
 - Under 2
 - 2 to less than 12
 - 12 to less than 18
 - 18 to less than 65
 - 65 and above

A table will be presented by treatment group and overall, by Age at informed consent (Pediatrics under 18 vs. Adults 18 and above), for the following variables:

- Ethnicity
- Race
- Sex

8.4 Disease Characteristics and Medical History

Summary statistics will be presented for the Efficacy Analysis Set by treatment group and overall, by age at informed consent (under 18 vs. 18 and above), for the following variables:

- Time at randomization since Glut1 DS diagnosis by mutation analysis
- Glut1 DS mutation description
- Glut1 DS symptoms history including whether ongoing: seizures, walking abnormality, coordination or motor abnormalities besides walking, paroxysmal exertional dyskinesia, movement disorder besides PED, cognitive abnormality, behavioral abnormality, developmental delay

- Ketogenic diet history (yes/no)
- Seizure history by type: Generalized Tonic-Clonic, Generalized Tonic, Generalized Clonic, Generalized Atonic, Partial/Focal with Secondary Generalization, Myoclonic, Myoclonic (Astatic) Atonic, Myoclonic Tonic, Complex Partial/Focal, Simple Partial/Focal Motor, Simple Partial/Focal Sensory, Simple Partial/Focal Psychological, Typical Absence, Atypical Absence, Absence with Special Features (Myoclonic absence), Absence with Special Features (Eyelid myoclonia), Unclassified (Inc. epileptic spasms)
- Average number of observable seizures (generalized [except absence] or partial-onset seizures) per month over the last 6 months

Listings will be provided for the following:

- Medical history: major illnesses, diagnoses, and surgeries

8.5 IP Administration

8.5.1 Study Drug Exposure

Duration of IP exposure and duration of UX007 exposure will be summarized by study period, and by treatment group, for subjects while taking UX007, and overall. A listing will also be provided.

8.5.2 Dose Titration

Summary statistics for dose titration will be presented by treatment group, and overall, for the Efficacy Analysis Set. The following parameters will be summarized:

- Missed Dose (Yes/No)
- Reason Dose Missed
- Total Daily Dose Taken (ml)
- Tolerability Issues (Yes/No)
- Target Dose (ml)

A listing will also be provided.

8.5.3 Diet Diary Review

The following measures will be summarized by visit based on the 3 day Diet Diary Review for the 3 days prior to each visit:

- Average Study Drug Calories, the average of the 3 entries for Study Drug

- Average Total Daily Calories
- Maximum Tolerated Dose Achieved (%)
- Maximum Tolerated Dose Achieved $\geq 20\%$ (yes/no)
- Prescribed Dose through next visit (ml)

A listing will also be provided.

8.5.4 Dosing Compliance

Number and percent of days missed will be summarized for the titration period, the double-blind placebo-controlled treatment period and the open-label extension period.

8.6 Efficacy Analyses

The statistical approach for each efficacy analysis is summarized in [Table 5](#) and will depend on the level of endpoint (primary, secondary, exploratory) and the study periods involved (double-blind placebo-controlled treatment, open-label extension). The statistical approach for Week 8 analyses of primary and secondary endpoints will be comparisons between UX007 and placebo. A more thorough table showing Test/Instrument, Eligible Study Population, Endpoint, Subjects Applicable, Endpoint Level, Timepoints for Assessments, and Statistical Approach by Study Period Analysis is provided in [Appendix A](#). The statistical approach is defined for the following study period analyses:

- Week 8 Analyses: incorporate data up to the end of the double-blind placebo-controlled treatment period
- Week 52 Analyses: incorporate data from the entire study

Each statistical approach is described in the following sections.

Table 5: Efficacy Analyses by Study Period and Endpoint Level

Endpoint Level	Statistical Approach: Week 8 Analyses	Statistical Approach: Week 52 Analyses
Primary and Secondary Endpoints	Comparison Between UX007 and Placebo Groups	Estimation by Treatment Group and Overall
Exploratory Endpoints	Summary Statistics by Treatment Group	Summary Statistics by Treatment Group and Overall
Exploratory Endpoints at Select Sites	Data Listing	Data Listing

